#### 6.12 Assessment & management of potential risk

Participants who develop CTCAE v5.0, Grade 3 or 4 serious adverse effects related to artesunate (or placebo) will be withdrawn from the study treatment but will continue in the study to enable an intention to treat analysis. The main possible risks associated with artesunate in this phase II trial are neutropenia and haemolytic anaemia. Patients should be monitored closely for these potential side effects and sites should take appropriate clinical action if such adverse events occur.

Defination of aanemie is a disorder characterized by a reduction in the amount of haemoglobin in 100 ml of blood. Signs and symptoms of anaemia may include pallor of the skin and mucous membranes, shortness of

breath, palpitations of the heart, soft systolic murmurs, lethargy, and fatigability. Patients developing anaemia as defines by CTCAE 5.0

- Grade 3 anaemia: Hgb <8.0 g/dL; <4.9 mmol/L; <80 g/L; transfusion indicated

- Grade 4 anaemia: Life-threatening consequences; urgent intervention indicated

The treatment for anaemia is blood transfusion.

Definition of neutropenia: A disorder characterized by an ANC <1000/mm3 and a single temperature of >38.3 degrees C (101 degrees F) or a sustained temperature of >=38 degrees C (100.4 degrees F) for more than one hour. Patients developing neutropenia as defines by CTCAE 5.0

- Grade 3 neutropenia: ANC <1000/mm3 with a single temperature of >38.3 degree C (101 degrees F) or a sustained temperature of >=38 degrees C (100.4. degrees F) for more than one hour
- Grade 4 neutropenia: Life-threatening consequences; urgent intervention indicated

Treatment for neutropenia is GCSF.

There will be a 24 hour emergency card provided to each participant when they receive their IMP dispensed from pharmacy. The 24 hour emergency card will contain the contact details of the local PI and site team in addition to a NeoART-M 24 hour emergency telephone number.

The IMP will be supplied double-blinded and IMP allocation will be performed by each site pharmacy or clinical resarch centre in accordance with the randomisation list provided by the sponsor's representative at the start of the study. In the case of a medical emergency each Pharmacy or CRC will have the ability to unblind treatment.

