#### Packaging and storage conditions

Study medication will be provided in bottles. One patient bottle will provide 28 tablets – sufficient for the duration of the study. The product labelling will be fully compliant with both Appendix E: Labelling Requirements of the Rules and guidance for Malaysian-Guideline-for-Application-of-CTIL-and-CTX-7.1-Edition and the protocol submitted and authorised by the NPRA.

Drug interactions with artesunate

There are no reports of negative drug interactions with artesunate to date.

Adverse events associated with artesunate

Artesunate is a safe drug that has been taken by millions of patients worldwide. In data taken from studies of malaria, serious side-effects are extremely rare.

The Summary of Product Characteristics for Artesunate provided to sites lists the potential side effects.

The reference safety information document provided to sites lists the adverse events considered by the Sponsor as being 'expected'.

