# 14. Pharmacovigilance

#### 14.1 Definitions

**Adverse Event (AE)** — Any untoward medical occurrence in a patient or clinical investigation subject administered a pharmaceutical product and which does not necessarily have to have a causal relationship with this treatment.

An adverse event (AE) can therefore be any unfavourable and unintended sign (e.g. an abnormal laboratory finding), symptom or disease temporally associated with the use of a medicinal product, whether or not considered related to the medicinal product. Pre-existing conditions should only be reported as an adverse event if the condition worsens by at least 1 CTCAE grade. As the IMP has a short half-life, we would expect drug clearance within 24 hours of stopping the IMP.

As part of pharmacovigilance, adverse event data will be collected from the day 1 of IMP dose until 4 weeks following the end of the IMP 14 day treatment schedule. This coincides with the D42 post surgical review.

**Adverse Reaction (AR)** — All noxious and unintended responses to a medicinal product related to any dose should be considered adverse drug reactions.

**Serious Adverse Event (SAE)** or Serious Adverse Reaction (SAR) — any untoward medical occurrence that at any dose:

- Results in death,
- Is life-threatening,
- Requires inpatient hospitalisation or prolongation of existing hospitalisation,
- Results in persistent or significant disability/incapacity or
- Is a congenital anomaly/birth defect.

Medical and scientific judgement should be exercised in deciding whether expedited reporting is appropriate in other situations, such as important medical events that may not be immediately lifethreatening or result in death or hospitalisation but may jeopardise the patient or may require intervention to prevent one of the other outcomes listed in the definition above. These should also usually be considered "serious".

Suspected Unexpected Serious Adverse Reaction (SUSAR) — an Adverse Reaction which is classed in nature as both serious and unexpected

An 'Unexpected Adverse Reaction' is when both the nature and severity of the event is not consistent with the reference safety information available for the IMP in question.

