**Unlikely** — there is little evidence to suggest there is a causal relationship (e.g. the event did not occur within a reasonable time after administration of the trial medication). There is another reasonable explanation for the event (e.g. the participant's clinical condition, or other concomitant treatments).

**Unrelated** — there is no evidence of any causal relationship.

**Not Assessable** — Note if this description is used the sponsor will assume the event is related to the IMP until follow up information is received from the investigator to confirm a definitive causality assessment.

Any SUSAR assessed as related to the IMP will need to be reported to the Sponsor irrespective of how long after IMP administration the reaction has occurred.

Expectedness should be based solely on the available RSI for the IMP and will be described using following categories :

**Expected** — an AE that is classed in nature as serious and which is consistent with the information about the IMP listed in the RSI or clearly defined in this protocol.

**Unexpected** — an AE that is classed in nature as serious and which is not consistent with the information about the IMP listed in the RSI.

The completed AE Log will be sent to Sponsor upon request and/or every 2 months.

The Chief Investigator (CI) will respond to any SAE queries raised by the Sponsor as soon as possible. Follow up reports must continually be completed within acceptable timeframes and sent to the sponsor as detailed above until the reportable event is considered resolved.

Notification of deaths

All deaths will be reported to the Sponsor irrespective of whether the death is related to disease progression, the IMP or an unrelated event.

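### Protocol Sections 14.1 and 14.2 define an unexpected reaction inconsistently, so the same serious reaction can be a SUSAR under one line and not under another

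*Protocol*

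**What the plan says.** Protocol Section 14.1 defines a SUSAR as "an Adverse Reaction which is classed in nature as both serious and unexpected". It then says that an unexpected adverse reaction "is when both the nature and severity of the event is not consistent with the reference safety information".

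Section 14.2 returns to the subject in three statements:

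- The basis: "Expectedness should be based solely on the available RSI for the IMP".
- The Expected category: a serious event that is "consistent with the information about the IMP listed in the RSI or clearly defined in this protocol".
- The Unexpected category: a serious event "which is not consistent with the information about the IMP listed in the RSI".

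Two other places bear on these rules. Section 8, in the text on adverse events associated with artesunate, describes the RSI as a separate document: "The reference safety information document provided to sites lists the adverse events considered by the Sponsor" as expected. Section 6.12 says: "The main possible risks associated with artesunate in this phase II trial are neutropenia and haemolytic anaemia". It goes on to define anaemia and neutropenia and to set out Grades 3 and 4 of each.

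**The concern.** A SUSAR must be both serious and unexpected, so the expectedness rule decides which related serious reactions become SUSARs. There are two faults in that rule.

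First, 14.1 asks for a departure in nature and in severity together, while the Unexpected line of 14.2 asks only for inconsistency with the RSI. The cases on which they can differ are known reactions at a new severity.

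Second, 14.2 makes the RSI the only reference and then, in its Expected line, adds the protocol as a second one. The Unexpected line does not mention the protocol, so the two categories can overlap.

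What is at stake is consistent classification. Two assessors who follow different lines of the same protocol can label the same case in opposite ways, and a tally of SUSARs could come out too low. The events most exposed to the second fault are those that the protocol itself describes, such as neutropenia and anaemia. Section 6.8 reports two pilot cases of Grade 3 neutropenia and anaemia, so such events are to be anticipated.

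**Working it through.** No figure is involved, so the check is to apply each rule literally to the kinds of related serious reaction that can arise.

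**Inputs.** The 14.1 definition of unexpected; the 14.2 basis, Expected and Unexpected lines; and the 14.1 SUSAR definition (serious and unexpected). The content of the RSI is not in the document, so what it lists is an assumption in each case.

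| Related serious reaction | 14.1 | 14.2 basis (RSI only) and Unexpected line | 14.2 Expected line |
|---|---|---|---|
| A. Nature listed in the RSI, severity greater than listed | Not unexpected: nature agrees, so the double condition fails | Unexpected, if consistency is taken to include severity | Not met on the same reading, unless the protocol defines the event |
| B. Absent from the RSI, defined in the protocol | Unexpected | Unexpected | Expected, through the protocol clause |
| C. Listed in the RSI at the observed severity | Not unexpected | Not unexpected | Expected |
| D. In neither the RSI nor the protocol | Unexpected | Unexpected | Not met |

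**Case A.** Under 14.1 the reaction is not a SUSAR. Under the Unexpected line of 14.2 it can be one. That line does not mention severity, so the conflict requires that the RSI conveys some severity and that an event worse than listed counts as not consistent with it. This is a natural reading of the line, but it is a reading.

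**Case B.** Under 14.1, and under both the basis and the Unexpected line of 14.2, the reaction is unexpected and so a SUSAR. Under the Expected line of 14.2 it is expected and so not a SUSAR. The two categories of 14.2 then hold at once. Whether any real event falls here depends on the RSI. The contradiction between a sole reference and an alternative reference is in the text whatever the RSI lists.

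**Cases C and D.** All lines agree. The disagreement is confined to A and B.

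**Effect on reporting.** Section 14.2 also requires SAEs and serious adverse reactions to be notified to the sponsor within 24 hours of the investigator becoming aware of them. It has the sponsor inform the regulator and the ethics committee of SAEs as well as SUSARs within 7 calendar days. Neither duty depends on expectedness. What changes in A and B is the SUSAR label, and with it the one duty tied to that label: "Any SUSAR assessed as related to the IMP will need to be reported to the Sponsor irrespective of how long after IMP administration".

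**The case against.** The strongest reply is that the practical effect is small. Because 14.2 sends SAEs and SUSARs alike to the regulator within 7 calendar days, the label changes no stated timeline. Deaths must be reported to the sponsor whatever their cause. It can also be said that the 14.1 sentence is loose drafting, meant to say that nature and severity must both agree for a reaction to be expected. The first part of this stands and limits the point to classification and counting. The second does not rescue the text: this is the definitions section, the sentence follows directly on the SUSAR definition, and a literal reader reaches the narrower rule.

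A reader might infer more than the document supports, in four ways.

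- **That affected events would go unreported.** The 24-hour and 7-day duties show otherwise.
- **That a late, non-fatal serious reaction classed as expected would have no reporting route once adverse event collection closes, 4 weeks after the end of treatment.** Section 14.1 limits the collection of adverse event data to that period, but the 24-hour duty in 14.2 has no stated end date. At most, the protocol leaves unclear whether that duty outlasts the collection period, which is a separate question.
- **That serious haemolytic anaemia would be classed as expected and lost as a SUSAR.** If the RSI lists it at the observed severity, expected is the proper class. If the RSI does not list it, the protocol clause must still apply. Section 6.12 names haemolytic anaemia as a risk but defines and grades anaemia in general, so whether it is clearly defined there is a matter of reading.
- **That the size of the conflict can be counted from a cross-table of nature by severity.** An unlisted event has no listed severity to agree with, so one cell is empty in practice. The count would also take for granted that the 14.2 wording covers severity.

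**Conclusion.** The point holds as an inconsistency in the stated rule, and the change should be made. Sections 14.1 and 14.2 give different tests for an unexpected reaction, and 14.2 contradicts itself on whether the RSI is the only reference.

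Two kinds of related serious reaction are affected: one of listed nature but greater than listed severity, and one defined in the protocol but absent from the RSI. For these, SUSAR classification depends on which line is applied, and SUSARs may be too few. The first conflict rests on reading consistency with the RSI as including severity. The second conflict in the text needs no assumption, but for an actual event to be caught by it, the RSI must omit something that the protocol defines. How many events this would involve cannot be estimated from the protocol.

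**What to change.** Use one definition in both sections: a serious reaction is unexpected when its nature or its severity is not consistent with the RSI. In the Expected line of 14.2, delete the alternative that admits events defined in the protocol, so that the line agrees with the sponsor's own rule that the RSI is the only basis.

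The cost is two wording changes in the next amendment. The downside is that slightly more events may be classed as SUSARs.

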#### 14.2 Investigator responsibilities relating to safety reporting

All Adverse Events whether serious or not will be recorded in the hospital notes in the first instance. A record will also be kept in the participant's CRF and the Sponsor's AE Log. In the event of a mildly deranged blood test or clinical observation of no clinical significance to the patient (for example a mildly elevated liver function test or a mildly elevated blood pressure reading in a participant with known hypertension taking prescribed antihypertensive medication), the local PI will be informed and will sign and date the participants CRF. However it will not be necessary to complete an AE CRF or the Sponsor's AE Log for these minor events.

SAEs and SARs must be notified to the sponsor as soon as the investigator becomes aware of the event (within 24 hours). Refer to sponsor's SOP and ensure the completed SAE report form is sent to the sponsor via E-mail.

The sponsor will inform the National Pharmaceutical Regulatory Agency (NPRA) and relevant ethics committee of SAE and SUSARs as soon as possible, but no later than 7 calendar days after first knowledge by the sponsor that a case qualifies. Any additional information will be reported within 8 additional calendar days. This report must include an assessment of the importance and implication of the findings, including relevant previous experience with the same or similar medicinal products. Follow-up information should be actively sought and follow-up reports should be submitted to the NPRA when it becomes available.

Causality Assessment — All cases judged by either the reporting health care professional or the sponsor as having a reasonable suspected causal relationship to the medicinal product qualify as ARs.

**Definitely** — there is clear evidence to suggest a causal relationship, and other possible contributing factors can be ruled out.

**Probably** — there is evidence to suggest a causal relationship and the influence of other factors is unlikely.

**Possibly** — there is some evidence to suggest a causal relationship (e.g. the event occurred within a reasonable time after administration of the trial medication). However, the influence of other factors may have contributed to the event (i.e. the patient's clinical condition, other concomitant events).

**Unlikely** — there is little evidence to suggest there is a causal relationship (e.g. the event did not occur within a reasonable time after administration of the trial medication). There is another reasonable explanation for the event (e.g. the participant's clinical condition, or other concomitant treatments).

**Unrelated** — there is no evidence of any causal relationship.

**Not Assessable** — Note if this description is used the sponsor will assume the event is related to the IMP until follow up information is received from the investigator to confirm a definitive causality assessment.

Any SUSAR assessed as related to the IMP will need to be reported to the Sponsor irrespective of how long after IMP administration the reaction has occurred.

Expectedness should be based solely on the available RSI for the IMP and will be described using following categories :

**Expected** — an AE that is classed in nature as serious and which is consistent with the information about the IMP listed in the RSI or clearly defined in this protocol.

**Unexpected** — an AE that is classed in nature as serious and which is not consistent with the information about the IMP listed in the RSI.

The completed AE Log will be sent to Sponsor upon request and/or every 2 months.

The Chief Investigator (CI) will respond to any SAE queries raised by the Sponsor as soon as possible. Follow up reports must continually be completed within acceptable timeframes and sent to the sponsor as detailed above until the reportable event is considered resolved.

Notification of deaths

All deaths will be reported to the Sponsor irrespective of whether the death is related to disease progression, the IMP or an unrelated event.

## 14.3 Development Safety Update Reports (DSURs)

The CI or the CI delegate will prepare the DSUR, using the Sponsor's template and in accordance with the Sponsor's DSUR SOP. It will be reviewed by the Sponsor and when necessary be referred to an independent committee (i.e. Research Governance Safety Sub Committee). The CI or the CI delegate will provide to the relevant ethics committee and the Sponsor will provide to NPRA the prepared DSUR annually within the defined reporting timelines.

## 14.4 Annual Progress/Safety Reports (APRs)

The CI or the CI delegate will prepare the APR in accordance with SOP. Following review by the Sponsor, the CI or the CI delegate will send to the relevant ethics committee to the reviewed report. The APR is due for submission annually within 30 days of the anniversary date on which the favourable opinion was given by the Ethics committee, until the trial is declared ended.

#### 14.5 Pregnancy

The limited data available on exposure during pregnancy does not indicate any adverse effects of artesunate on the health of the foetus/newborn child. However, there is inadequate information for determining the foetal risk of artesunate treatment during pregnancy. Data from preclinical embryo foetal development studies in rats and rabbits showed a low incidence of cardiovascular malformation and syndrome of skeletal defects at doses close to embryolethal doses starting at around 6mg/kg/day. The dose used in our study of artesunate 200 mg will be below this threshold. In the event that pregnancy occurs whilst on the study drug, the pregnancy will be recorded in both the participant notes and CRF, the Sponsor and DMC will be notified. The female participant/pregnant partner of a male participant will be urgently reviewed by the research team and obstetric specialist and emergency un-blinding of the trial arm will be undertaken as per protocol section 11.4. If the participant is found to be receiving artesunate, the female participant or pregnant partner of a male participant will be followed up closely on a fortnightly basis together with an Obstetric Specialist and Foetal Medicine Specialist. The pregnancy will be monitored closely for any intrauterine abnormalities. Following successful delivery the newborn child will be monitored for up to 12 months together with a Paediatrician to ensure no adverse developmental effects have occurred.

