#### Pregnancy

Artesunate is teratogenic in animal models and is contraindicated in the first trimester of pregnancy in humans. Pregnant women with malaria nevertheless are exposed to artesunate when no alternatives are available for treatment and studies published to date do not indicate an increased risk of teratogenicity. Pregnant women will not be recruited and participants will be required to use effective methods of medical contraception during the study. Women of child bearing age will be required to undergo a pregnancy test within 72 hours prior to commencing the study and must consent to adequate contraceptive methods from the time of consent and for up to 6 weeks following the end of treatment. Male participants with a partner of childbearing potential must agree to use adequate, medically approved contraceptive precautions from the time study consent is signed till up to 6 weeks after the last dose of study treatment intervention. Methods of contraception that are acceptable for the trial include the following:

The implant, the coil and male or female sterilisation will be acceptable for the trial. The injection and most forms of hormonal contraception will also be deemed acceptable for the trial if used in combination with condoms or other barrier methods. However, condoms alone won't be sufficient during the study.

IMPs and non-IMPs used in the trial

Patients entered into the study will be randomised to receive artesunate 200 mg (administered as 2 x 100mg tablets) or identical matching placebo once a day orally for 14 days.

Dosage modifications

No dosage modifications will be undertaken. Any Grade 3/4 reaction (according to Common Terminology Criteria for Adverse Events (CTCAE) Version 5.0) which occurs in any patient and is deemed related to the IMP or placebo by the treating investigator will result in that patient's trial treatment being discontinued.

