#### 9.1 Inclusion criteria

- 1. Aged 18 or over
- 2. Histologically proven single primary site colorectal adenocarcinoma or high grade dysplasia plus unequivocal radiological evidence of invasive cancer
- 3. Stage II/III colorectal cancer planned for surgical resection and no clinical indication for neoadjuvant preoperative chemotherapy/chemoradiation therapy
- 4. WHO performance status 0,1 or 2
- 5. Adequate full blood count: White Cell Count (WCC)  $>3.0 \times 10^9$  /l; Platelets  $>100 \times 10^9$ /l; Haemoglobin (Hb) >80g/L
- 6. Adequate renal function: Glomerular Filtration Rate >30ml/min by Cockcroft-Gault formula.
- 7. Adequate hepatobiliary function: Total bilirubin < 3 x Upper limit norm
- 8. Female participants of child bearing potential must have a negative pregnancy test <72 hours prior to initiating study intervention and agree to avoid pregnancy using adequate, medically approved contraceptive precautions for up to 6 weeks after the last dose of study treatment interventions.
- 9. Male participants with a partner of childbearing potential must agree to use adequate, medically approved contraceptive precautions during and for up to 6 weeks after the last dose of the study treatment intervention.
- 10. Patient able and willing to provide writen, informed consent for the study.

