#### 12.3 Treatment procedure

[Refer to Appendix 2 for a summary chart of study assessments]

Participants entered into the study will be randomised 1:1 to receive artesunate 200 mg or matched placebo once a day orally for 14 days to commence 15 days prior to day of scheduled surgery. The artesunate/placebo packs dispensed to the participant will provide clear instructions on when to start taking the IMP and when to stop.

Study medication will be started fifteen days before the scheduled surgery with the final dose taken on Day 14 (the day before surgery).

Day 7 of study medication (telephone assessment)

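### Section 14.5 requires recording and notification only of a pregnancy that occurs on study drug (14 days), while the protocol requires contraception until 6 weeks after the last dose (Day 56)

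*Protocol*

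**What the plan says.** Section 14.5 of the protocol opens its procedure with a condition: "In the event that pregnancy occurs whilst on the study drug, the pregnancy will be recorded in both the participant notes and CRF". The same sentence provides for notice to the Sponsor and the DMC. Urgent review and emergency unblinding come next, for a participant or a male participant's partner. Obstetric follow-up then depends on a second condition, in the present tense: "If the participant is found to be receiving artesunate".

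The treatment is short. Section 12.3 has it given "once a day orally for 14 days to commence 15 days prior to day of scheduled surgery".

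The contraception requirement runs longer. Under section 9.1, women must "agree to avoid pregnancy using adequate, medically approved contraceptive precautions for up to 6 weeks after the last dose of study treatment interventions", and men with a partner who could conceive must use "contraceptive precautions during and for up to 6 weeks after the last dose of the study treatment intervention". The Pregnancy text in section 8 says that women of childbearing age "must consent to adequate contraceptive methods from the time of consent and for up to 6 weeks following the end of treatment", and sets the same end point for men. The synopsis repeats these criteria, and the contraception exclusion in section 9.2 also runs to 6 weeks after the last dose.

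For safety data in general, section 14.1 sets this window: "adverse event data will be collected from the day 1 of IMP dose until 4 weeks following the end of the IMP 14 day treatment". It ties that end point to the Day 42 post-surgical review.

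**The concern.** The protocol asks participants to avoid pregnancy for 6 weeks after dosing, but its pregnancy rule speaks only of the dosing period. A site that follows section 14.5 as written would have no instruction to record, or to tell the Sponsor or the DMC about, a pregnancy that begins on Day 20, or a partner's pregnancy that begins on Day 50. Both would fall inside the period for which the protocol asks for precautions.

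What is at stake is the completeness of a small but sensitive part of the safety record. Section 8 notes teratogenicity in animal models, and section 14.5 itself says that too little is known to determine the risk to the foetus. A final report that lists no pregnancies should mean that none occurred in the precaution period. Under the present wording it could mean only that none was reported from the 14 days of dosing.

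**Working it through.** There is no published figure to reproduce. The check is a day count and a comparison of sections.

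**Inputs**
- Dosing: 14 days, Days 1 to 14 (section 12.3).
- Contraception after the last dose: 6 weeks (synopsis; sections 8, 9.1 and 9.2).
- End of adverse event collection: 4 weeks after the 14-day course (section 14.1).
- Visit window for the Day 42 review: 2 weeks either side (section 12.3 and Appendix 2).

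**Day count**
- Contraception tail: 6 × 7 = 42 days, Days 15 to 56.
- First dose to end of contraception period: 14 + 42 = 56 days.
- Share covered by the section 14.5 trigger: 14 / 56 = 25%.
- Share without a pregnancy rule: 42 / 56 = 75%.
- Nominal end of adverse event collection: Day 14 + 28 = Day 42. Nominal gap to the end of the contraception period: 56 − 42 = 14 days.
- Latest permitted date of the Day 42 review: 42 + 14 = Day 56. For a participant reviewed that late, the nominal gap closes.

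**Does another provision cover the 42 days?**

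| Provision | Reach | Covers a pregnancy in Days 15–56? |
|---|---|---|
| Adverse event collection (14.1) | Nominally to Day 42 | Pregnancy is not named. An adverse event is defined for the person given the product, so a partner's pregnancy is not one on any day |
| Serious adverse event criteria (14.1) | Birth defect is listed | Concerns an outcome, not a pregnancy |
| Related SUSARs (14.2) | No time limit | Concerns a suspected reaction, not a pregnancy |
| Medical history (12.3, Appendix 2) | Day 42, then 6-monthly | General history only; no pregnancy item is listed |
| Pregnancy test (8, 9.1, 12.2) | Before treatment | No |

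None of these states how a pregnancy in Days 15 to 56 is to be recorded or notified. For partners, section 14.5 is the only route in the document.

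**The case against.** The strongest reply is that the two sets of provisions do different jobs. Contraception is an undertaking given at entry, with a margin built in, while section 14.5 deals with pregnancies that overlap with treatment. A site can comply with both, so they do not contradict each other outright. This stands. The point is a mismatch of periods and a silence about the difference.

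Several stronger readings are tempting, and the documents do not support them.

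- *That drug exposure would be missed.* Section 8 gives plasma half-lives of 3 to 29 minutes for artesunate and 40 to 95 minutes for its active metabolite. Section 14.1 expects clearance within 24 hours, which is about 15 of the longest of those half-lives (1,440 / 95 = 15.2). On these figures, a conception on Day 20 or Day 50 is not shown to be an exposed one.
- *That the protocol regards the 6 weeks as unsafe.* It never says so and gives no reason for that length. Section 8 adds that published human studies do not point to an increased teratogenic risk. The 25% therefore describes calendar time and cannot be read as a share of risk.
- *That Days 43 to 56 lie outside all data collection.* That is the nominal position, but the Day 42 review to which adverse event collection is tied may take place as late as Day 56.
- *That a pregnancy begun during dosing but recognised later would escape the rule.* The trigger turns on when the pregnancy occurs, so such a case still meets it. It would help to say so explicitly, since the follow-up condition is worded in the present tense, but the text as it stands does not exclude the case.

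It is also true that the case report forms and the Sponsor's safety procedures are not among the documents and may contain more. But the rule that the protocol itself states is the narrow one.

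**Conclusion.** The point holds as a mismatch between the pregnancy-recording trigger and the protocol's own contraception period. The trigger covers 14 of 56 days, and for the remaining 42 days no provision says how a participant's or partner's pregnancy is recorded or notified. The count assumes that dosing runs Days 1 to 14 as scheduled and that the 6 weeks are counted from the last dose.

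The consequence is modest. No efficacy endpoint or analysis is affected. The number of participants concerned is probably small, although the documents give no figure for it. The documents do not show that any drug exposure would go unseen. It is still worth correcting: the change is cheap, partners have no other reporting route, and the protocol itself says that information on foetal risk is inadequate.

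**What to change.** Reconcile section 14.5 with the synopsis and sections 8, 9.1 and 9.2. Recording, and notification of the Sponsor and the DMC, should follow the contraception period that the protocol itself sets, for pregnancies in participants and in partners alike, and should apply whenever the pregnancy is recognised. Add a pregnancy question, covering the participant and any partner, at the existing Day 42 and 6-month visits.

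The unblinding and clinical follow-up provisions in section 14.5 depend on the same opening condition, so the sponsor must reconcile them with those sections as well. No view is offered here on which clinical period or management is right.

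The cost is one amended sentence and one case report form item. No new visit is needed.
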